6.2.2 Treatment Strategy for Ablation

Selected sites use a PVI-only strategy as standard of care for all de novo ablation of AF. After completing the mapping protocol, ablate the pulmonary vein antrum to isolate the veins using a wide area circumferential ablation (WACA) technique⁸ with the TactiCath™ Contact Force Ablation Catheter, Sensor Enabled™ (TactiCath SE). If isthmus dependent flutter is identified and confirmed by electrophysiological testing (e.g. entrainment maneuvers), ablation of the cavo tricuspid isthmus is recommended in the right atrium. No deviations from standard of care⁹ should be performed unless medically necessary. The AutoMark™ feature should be turned on for automated lesion-level data capture based on user-defined settings. Event Markers should be used to note physician comments about changes in rhythm¹⁰.

PVI should be confirmed bidirectionally using the GRID and confirmed after a recommended 20-minute wait time to ensure isolation is achieved. In addition, use of isoproterenol or adenosine are allowed per the investigator's discretion to confirm block.

If arrhythmias remain after pulmonary vein isolation, it is recommended to treat with cardioversion and/or medication unless there is a medical necessity to perform additional ablation.

6.3 Post-Procedure and Early Follow Up

Sites should follow standard of care for use of AAD during the blanking period to address symptoms during healing. It is recommended to exclude Amiodarone due to its long half-life, since the effects of amiodarone could continue past the blanking period impacting recurrence rates.

All other aspects of care should follow the site's standard practice from discharge through the end of the 3-month blanking period.

6.4 Follow-up Assessments

The following sections describe the follow-up visits and procedures. All windows are stated with respect to the index procedure unless otherwise noted. It is recommended to follow the HRS Consensus guidelines for follow-up screening depending on type of AF (e.g. paroxysmal vs. persistent). A 12-lead

⁸ This may include ablation to address the carina within the WACA circle per the investigator's discretion.

⁹ Site's standard of care is PVI-only, so no other substrate modification should be performed.

¹⁰ For example, "AF resolved to sinus rhythm during ablation of lesion #23".

Clinical Investigation Plan

ECG is recommended any time the subject returns to the clinic from 3- to 12-months post index procedure.

6.4.1 3-Month Follow Up (77 to 105 Days Post Index Procedure)

The blanking period ends on the day of the 3-month follow up visit. It is recommended the subject not be taking any class I or III AAD after the 3-month visit unless there is recurrence of AF. At the 3-month visit, the following procedures will be completed:

- Check for symptoms of recurrence
- Perform 12-lead ECG
- Document Adverse Events and Protocol Deviations
- Document AAD usage
- Document any recurrences including any details of repeat electrophysiology studies
- Instruct the subject to contact the site if they experience any symptoms of recurrence. If there are any symptoms noted after the 3-month visits through the 12-month visit, check for recurrence using 12-lead ECG or other form of monitoring per site's standard practice.

It is also recommended to provide the subject with an event monitor for recording at regular intervals (e.g. monthly) or for symptomatic events through the 12-month visit.

After the 3-month visit through the end of the study, any signs or symptoms of recurrence should be recorded, and the subject should have either a 12-lead ECG or other form of ECG monitoring per the site's standard practice to determine if recurrence has occurred.

6.4.2 6-Month (169 to 197 Days) Follow Up Phone Visit

Within two weeks of the 6-month time point post index procedure, the subject will be contacted via telephone (or seen in-clinic if standard of care) for the following assessments

- Check for symptoms of recurrence
- Document Adverse Events and Protocol Deviations
- Document AAD usage
- If there are symptoms of recurrence present, the subject should have either a 12-lead ECG or other form of ECG monitoring to determine if recurrence has occurred.
- Document any recurrences including details of any repeat electrophysiology studies

For persistent AF subjects, it is also recommended that a 24-hour holter be performed at the 6-month time point.

6.4.3 12-Month Follow Up Visit (335 to 395 Days Post Index Procedure)

The 12-Month visit will include the following procedures:

- Check for symptoms of recurrence
- Perform 12-lead ECG

Clinical Investigation Plan

- Record Adverse Events and Protocol Deviations. Make sure to record the status of each ongoing event at the time of study exit.
- Document AAD usage
- Complete 24-hour continuous ECG monitoring¹¹, and record results on the applicable CRF
- Document any recurrences including any details of repeat electrophysiology studies

¹¹ This does not have to be done on the day of the visit. It can be done any time during the 12-month visit window.

[REDACTED]

Clinical Investigation Plan

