4.0 ENDPOINTS

4.1 Primary Endpoint and Rationale

The primary outcome is one-year success, defined as freedom from AF/AFL/AT after removal from antiarrhythmic drug therapy as assessed from the end of the 3-month blanking period to 12 months following a single ablation procedure.

Occurrence of isthmus-dependent atrial flutter, if confirmed during electrophysiology testing, should not be considered a failure for this outcome.

This endpoint is based on the recommendations from the 2017 HRS consensus paper.¹⁸

Clinical Investigation Plan

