ablation for atrial fibrillation: a randomized study	without linear ablation depending on the type of AF.	Treatment: PVI plus ablation of low-voltage areas			arrhythmia recurrence >30 s off antiarrhythmic drugs (AADs) after a single procedure (primary endpoint) compared with control group patients [40/59 (68%) vs. 25/59 (42%), log-rank P = 0.003]. Arrhythmia-free survival on or off AADs was found in 33/59 control group patients (56%) and in 41/59 LVA ablation group patients (70%) (adjusted log-rank P = 0.10). During the 7 day Holter monitoring period at 12 months, significantly more patients in the LVA ablation group were free from arrhythmia recurrence on or off AADs [45/50 (90%) vs. 33/46 (72%), P = 0.04].
Jadidi, et al ²⁴ Ablation of Persistent Atrial Fibrillation Targeting Low-Voltage Areas With Selective	Determine if PVI plus ablation of selective atrial low-voltage sites may be	Group 1: PVI plus ablation of low-voltage areas Group 2: Matched control of 66	85 consecutive persistent AF patients	Single procedure arrhythmia freedom	Single-procedural freedom at 13 months median follow-up was 59/85 (69%) in group 1 compared to 31/66

Clinical Investigation Plan

Clinical Investigation	Objective	Study Arms	Patient population	Endpoints	Results
Activation Characteristics.	more successful than PVI only	patients with PVI only			(47%) in group 2 (p<0.001)
Schreiber, et al ²⁵ Catheter ablation of atrial fibrillation with box isolation of fibrotic areas: Lessons on fibrosis distribution and extent, clinical characteristics, and their impact on long-term outcome	Report outcomes using box isolation of fibrotic areas (BIFA) in patients with fibrotic atrial cardiomyopathy (FACM)	Retrospective analysis compared PVI + BIFA (n=92) to non-fibrosis reference group with PVI only (n=49)	92 de novo persistent and paroxysmal patients with PVI + BIFA based on detection of significant fibrotic areas defined as <0.5mV	Arrhythmia free	For BIFA ablation, single and multiple procedure arrhythmia-free survival was 68.8% and 82.8% with 1.2 procedures/patient and a follow-up time of 16.3 ± 8.2 months after the index procedure. FACM+II pts showed a significantly better outcome compared to FACM III+IV pts (single procedure: 81.0 vs. 40.9%, P < 0.001, multiple procedure 92.8 vs. 61.4%, P < 0.001). Non-fibrosis reference group had single/multiple procedure success rates of 84.4% and 93.7% respectively with 1.1 procedures.

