### 2.4 Endpoint and Additional Data

#### 2.4.1 Primary Endpoint

The primary outcome is one-year success, defined as freedom from AF/AFL/AT after removal from antiarrhythmic drug therapy as assessed from the end of the 3-month blanking period to 12 months following a single ablation procedure.

Occurrence of isthmus-dependent atrial flutter, if confirmed during electrophysiology testing, should not be considered a failure for this outcome. This endpoint is based on the recommendations from the 2017 HRS consensus paper.

[REDACTED]

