##### **3.1.3 Survival Analyses**

Survival (SURV) analysis will be conducted to analyze time-to-event variables. Subjects without events will be censored at their last known event-free time point. Subjects withdrawn or otherwise lost-to-follow-up during the follow-up period will be censored at their last known visit. Survival data will be presented using the Kaplan-Meier product limit method. Number of subjects at risk, number of censored subjects, number of events, event free survival rate and standard error of the survival rate at each follow-up time point will be presented in a summary table.

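### Does the plan count subjects who stay on antiarrhythmic drugs as successes, although the primary endpoint requires being off them?

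*Protocol*

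**What the plan says.** The primary endpoint has the same wording in both documents. Protocol 4.1 asks for "freedom from AF/AFL/AT after removal from antiarrhythmic drug therapy as assessed from the end of the 3-month blanking period to 12 months" after one ablation, and SAP 2.4.1 repeats it: "The primary outcome is one-year success, defined as freedom from AF/AFL/AT after removal from antiarrhythmic drug therapy". The drug condition is part of the definition.

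Drug care is left to the sites. For the first three months Protocol 6.3 states: "Sites should follow standard of care for use of AAD during the blanking period to address symptoms during healing". From the 3-month visit on, Protocol 6.4.1 has only a recommendation: "It is recommended the subject not be taking any class I or III AAD after the 3-month visit unless there is recurrence of AF". Table 2 of the protocol makes recording of antiarrhythmic drugs a required item at 3, 6 and 12 months.

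The visible time-to-event text (Protocol 8.2, SAP 3.1.3) reads: "Subjects without events will be censored at their last known event-free time point". SAP 3.1.4 adds that logistic regression will be used; the rest of that section is blacked out.

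**The concern.** An endpoint that requires subjects to be off drugs, alongside a protocol that does not require them to stop, leaves a group to be classified: arrhythmia-free subjects still taking a class I or III drug after month 3. If the event is taken to be arrhythmia alone, SAP 3.1.3 carries such a subject event-free to 12 months, and the drug condition has no effect. The primary endpoint would then be the same as the unconditional freedom from AF/AFL/AT in SAP 2.4.2.

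Two things would be at stake. The success rate would be too high. The primary objective, the association between low-voltage substrate and recurrence, could also be distorted: the investigator has acquired the map, and if subjects with more low-voltage tissue were kept on drug more often, their failures could be masked and the association weakened.

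**Working it through.** The plan gives no figure to reproduce here. The sample size sections are redacted, and SAP 3.3.3 says no hypothesis will be tested. The check is therefore mainly a comparison of passages.

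**1. Is there an arrhythmia-only event rule?** No. SAP 3.1.3 is a general description of Kaplan-Meier analysis for any time-to-event variable. It does not define an event and is not tied to the primary endpoint. The list assigning methods to the primary endpoint (the PTE part of Protocol 8.2 and SAP 3.2.4) is blacked out.

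**2. What does the endpoint's own wording imply?** "freedom from AF/AFL/AT after removal from antiarrhythmic drug therapy as assessed from the end of the 3-month blanking period" is not met, read literally, by someone still on the drug. A generic censoring sentence does not override it.

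**3. Did the authors separate the drug conditions?** Yes. SAP 2.4.2 lists a symptomatic version off drugs, a version without a new or increased class I/III dose, and freedom from AF/AFL/AT with no drug condition. The last does not appear in the corresponding list in Protocol 4.2; the SAP adds it. Listing it as an additional outcome makes sense only if the primary endpoint differs from it.

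**4. Can the condition be applied?** Yes. Drug use is recorded at 3, 6 and 12 months. Leaving treatment to the sites and applying the drug condition when the endpoint is scored is coherent.

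**5. Who is affected?** Subjects given a drug because of a documented recurrence after blanking have already failed. Only event-free subjects on drug remain.

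**6. Where would the rule sit?** SAP 2.4.1 is blacked out directly after the endpoint definition. So are most of SAP 3.1.4, the population definitions (Protocol 8.1, SAP 3.2.1), the PTE analysis lists and the success criteria (Protocol 8.10).

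**7. Does the literature table give a size?** Protocol Appendix IV reports a randomized study of two ablation strategies. Off drugs the result was "40/59 (68%) vs. 25/59 (42%), log-rank P = 0.003"; on or off drugs it was 41/59 vs 33/59.

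| Scoring | Low-voltage ablation | Control | Gap |
|---|---|---|---|
| Off drugs | 40/59 = 67.8% | 25/59 = 42.4% | 15/59 = 25.4 points |
| On or off drugs | 41/59 = 69.5% | 33/59 = 55.9% | 8/59 = 13.6 points |
| Shift | 1/59 = 1.7 points | 8/59 = 13.6 points | |

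The percentages agree with the table. But the gap is a contrast between treatments, and the control arm included linear ablation for persistent AF. It is not an association between substrate and recurrence after PVI alone. The P values are not like for like either: 0.003 is a log-rank P, whereas 0.10 is an adjusted log-rank P.

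**8. What could the choice of rule do here?** Let *a* be the arrhythmia-free share and *d* the share of those still on drug. Both are assumptions.

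- On-drug subjects scored as successes: *a*
- Scored as failures: *a*(1 − *d*)
- Excluded: *a*(1 − *d*) / (1 − *ad*)

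With *a* = 0.70 and *d* = 0.10 these give 70.0%, 63.0% and 0.63/0.93 = 67.7%. With *d* = 0.20 they give 70.0%, 56.0% and 0.56/0.86 = 65.1%. Over *a* = 0.60–0.80 and *d* = 0.05–0.20, failure scoring differs from success scoring by *ad*, from 0.60 × 0.05 = 3 points to 0.80 × 0.20 = 16 points.

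**The case for a change.** The strongest contrary case is that Protocol 4.1 shows no redaction and already contains one scoring exception, for confirmed isthmus-dependent flutter, but nothing on subjects still on drug. The protocol summary (Appendix X) has nothing either. The SAP shows that its authors could write an explicit drug rule, since one of the additional outcomes has one. Protocol 6.3 itself recognises that amiodarone could affect recurrence rates beyond blanking. And because stopping is only recommended, an event-free subject kept on drug may not appear as a protocol deviation.

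What stands is limited: the visible text does not state how these subjects are classified, and step 8 shows that the classification can matter. That is unseen detail, not a demonstrated error. The SAP is the natural place for a scoring rule, and the text immediately after its endpoint definition is blacked out.

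The bias argument is conjecture on direction, since no passage links drug decisions to the maps. Nor do the endpoint's words dictate one remedy. Failure, censoring and exclusion are all compatible with them. Blanking ends on the day of the 3-month visit, so failing any later use would make a permanent failure of a subject who stopped a few days afterwards and stayed free of arrhythmia. If drug decisions did follow the map, failure scoring would build the exposure into the outcome and could inflate the association.

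**Conclusion.** The concern does not hold. Following the plan as written does not turn an on-drug subject into a success: the drug condition is in the endpoint, the unconditional version is a separate outcome, and the data needed to apply the condition are collected. The sentence taken as the event rule neither defines the event nor mentions drugs.

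The documents do not support a size for any effect. The 13.6-point shift belongs to another design, and the 3 to 16 points depend on assumed shares of arrhythmia-free and on-drug subjects. The conclusion rests on reading the endpoint literally and on not treating redacted text as absent. It does not establish which classification the redacted text contains.

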6.4.4 Schedule of Events

The following tables summarizes the schedule of events.

Table 2 Summary of Clinical Investigation Procedures

CIP Activity	Enrollment/ Baseline (within 14 days of index procedure)	Index Procedure	3-Month (77 to 105 Days)	6-Month phone call (169 to 197 Days)	12-Month (335 to 395 Days)
Informed Consent Process	X				
Record Height and Weight	X				
Demographics	X				
Medical History	X				
NYHA assessment	X				
Record AAD	X		X	X	X
Thrombus assessment per SOC	X	(X)			
Mapping Protocol		X			
PVI		X			
Submit EnSite Data		X			
Transthoracic Echo (TTE)	X				
12-lead ECG	X		X	Y	X
Pregnancy Test	(X)				
Symptom check			X	X	X
Check/Document Recurrence			(X)	(X)	(X)
24-hour continuous ECG				Y ¹²	X
Event recording ¹³			Y	Y	Y
Adverse Event	(X)		(X)	(X)	(X)
Deviation	(X)		(X)	(X)	(X)
Withdrawal	(X)		(X)	(X)	(X)
Death	(X)		(X)	(X)	(X)

(X) if applicable

X = required

Y = recommended

7.0 ADVERSE EVENTS

To comply with worldwide standards and guidelines on clinical investigation adverse event reporting, the Sponsor has adopted uniform and worldwide applicable standard definitions and reporting timelines to be used and adhered to by the investigators.

¹² A 24-hour holter is recommended for persistent AF subjects at 6 months post ablation procedure.

¹³ Event recording is recommended at regular intervals from 3 to 12 months post ablation procedure and for symptomatic events.

Clinical Investigation Plan

7.1 Definition

7.1.1 Adverse Event

An adverse event (AE) is any untoward medical occurrence, unintended disease or injury, or untoward clinical signs (including abnormal laboratory findings) in subjects, users or other persons, whether or not related to the medical device under investigation.

This definition includes events related to the medical device(s) under investigation and the mapping/ablation procedures involved. For users or other persons, this definition is restricted to events related to the medical devices under investigation.

7.1.2 Serious Adverse Event

If the AE meets any of the criteria below, it is regarded as a serious adverse event (SAE).

- a) Led to a death,
- b) Led to a serious deterioration in health of the subject, that either resulted in
 1. a life-threatening illness or injury, or
 2. a permanent impairment of a body structure or a body function, or
 3. in-patient hospitalization or prolongation of existing hospitalization, or
 4. medical or surgical intervention to prevent life threatening illness or injury or permanent impairment to a body structure or a body function.
 5. chronic disease
- c) Led to fetal distress, fetal death or a congenital abnormality or birth defect.

Note: A planned hospitalization for pre-existing condition, or a procedure required by the CIP, without a serious deterioration in health, is not considered to be an SAE.

7.2 Device Relationship

Determination of whether there is a reasonable possibility that a device under investigation caused or contributed to an AE is to be **determined by the Investigator** and recorded on the appropriate CRF form. Determination should be based on assessment of temporal relationships, evidence of alternative etiology, medical/biologic plausibility, and patient condition (pre-existing condition).

7.3 Adverse Event

7.3.1 Adverse Event Reporting

Safety surveillance and reporting starts as soon as the patient is enrolled in the clinical investigation. Safety surveillance and reporting will continue until the last follow-up visit has been performed, the subject is deceased, the subject concludes participation in the clinical investigation or the subject withdraws from the clinical investigation. Adverse event data, including deaths, will be collected

Clinical Investigation Plan

throughout the time period defined above and will be reported to the Sponsor on a CRF. Additional information with regard to an adverse event should be updated within the appropriate CRF.

Unchanged, chronic, non-worsening, or pre-existing conditions are not AEs and should not be reported.

An offline form will be made available to allow the investigator to report SAEs in the event the entry cannot be made in the EDC. This does not replace the EDC reporting system. All information must still be entered in the EDC system as soon as feasible.

Non-cardiac related abnormal laboratory values will not be considered AEs unless:

1. the investigator determined that the value is clinically significant,
2. the abnormal lab value required intervention, or
3. the abnormal lab value required subject withdrawal from the clinical investigation.

For the purposes of this clinical investigation, the following events will be reported:

- Adverse events that are considered to be related to any of the study devices or the mapping/ablation procedure by the investigator
- Serious adverse events resulting in death

Recurrence of AF, AFL, or AT are not considered reportable adverse events unless they occur in a severity, frequency, or other manner that is significantly worse than the subject's baseline condition. These are considered lack of effectiveness and will be reported as a recurrence on the appropriate case report form.

The investigator should report all SAEs to the Sponsor as soon as possible but no later than outlined below.

SAE Reporting

The investigator should report applicable SAEs to the Sponsor as soon as possible but no later than outlined below.

Clinical Site	Reporting timelines
All Sites	SAEs must be reported to the Sponsor no later than 3 calendar days from the day the site personnel became aware of the event or as per the investigative site's local requirements, if the requirement is more stringent than those outlined above.

The date the site staff became aware the event met the criteria of an SAE must be recorded in the source document. The Investigator will further report the SAE to the local EC according to the institution's EC reporting requirements.

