5.4 Subject Enrollment

A patient is considered enrolled in the clinical investigation from the moment the patient provides written informed consent, has been confirmed to meet all inclusion criteria and none of the exclusion criteria and has had the mapping catheter inserted into the subject's vasculature.

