11.4 Case Report Form Completion

Primary data collection based on source-documented hospital and/or clinic chart reviews will be performed clearly and accurately by site personnel trained on the CIP and CRF completion. The investigator will ensure accuracy, completeness, legibility and timeliness of the data reported to the Sponsor on the CRFs and in all required reports.

Data on CRFs will be collected for all subjects that are enrolled into the clinical investigation.

Only authorized site personnel will be permitted to enter the CRF data through the EDC system deployed by the Sponsor. An electronic audit trail will be used to track any subsequent changes of the entered data.

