15.2 Foreseeable Adverse Events and Anticipated Adverse Device Effects

The most commonly known risks for any ablation procedure are listed below:

- Bleeding or infection at the site where your catheter was inserted
- Damage to your blood vessels where the catheter may have scraped as it traveled to your heart
- Puncture of your heart
- Damage or swelling to the sack which surrounds your heart, making it difficult for the heart to beat strongly
- Damage to your heart valves
- Damage to your heart's electrical system, which could worsen your arrhythmia and could require a pacemaker to correct
- Blood clots in the legs or lungs (venous thromboembolism);
- Stroke or heart attack
- Narrowing of the veins that carry blood between your lungs and heart (pulmonary vein stenosis)
- Damage to your kidneys from dye used during the procedure
- Low blood pressure

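### The protocol starts adverse event reporting at mapping catheter insertion, so procedure-related events before that moment carry no clear reporting duty, and Table 2 points the other way

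*Protocol*

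**What the plan says.** Protocol 7.3.1 sets the start of the safety window: "Safety surveillance and reporting starts as soon as the patient is enrolled in the clinical investigation". Event data are then collected "throughout the time period defined above and will be reported to the Sponsor on a CRF".

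Protocol 5.4 defines enrolment by three conditions: written consent, confirmed eligibility, and that the patient "has had the mapping catheter inserted into" the vasculature. The third condition is met last, during the index procedure.

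Protocol 7.3.1 lists what is reportable. Besides serious events resulting in death, the list contains "Adverse events that are considered to be related to any of the study devices or the mapping/ablation procedure by the investigator".

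Protocol 11.4 ties data capture to the same status: "Data on CRFs will be collected for all subjects that are enrolled into the clinical investigation".

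Protocol 8.2 and SAP 3.2.4 tabulate adverse events, expressly including procedure-related ones, in the ENR (Enrolled) population. The definition of that population is redacted in both documents.

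Table 2 of the protocol (section 6.4.4) marks Adverse Event, Deviation, Withdrawal and Death as applicable under Enrollment/Baseline, a column that precedes catheter insertion.

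**The concern.** The index procedure begins before the mapping catheter goes in. Anaesthesia or sedation and venous puncture come first, and either can harm a consented subject. If the reporting window opens only at insertion, such an event falls before it, although the protocol intends procedure-related events to be reported.

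The loss would also be selective. A complication serious enough to stop the procedure before insertion is the very thing that prevents enrolment, so the subject would drop out of both numerator and denominator. Section 1.0 says the study is meant to support marketing claims for the catheter, so a procedure-related event rate from it should rest on a clear numerator and denominator.

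**Working it through.** The plan states no event rate, and its sample size sections are redacted, so there is no figure to reproduce. The check is mainly a reading of the sections against one another.

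**Step 1: three cases under the literal rules (5.4, 7.3.1, 11.4).**

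- *Event first appears or worsens after insertion.* The subject is enrolled and the window is open. The event is reportable if judged related. This covers, for example, a later haematoma or access-site infection. It also covers ablation complications, because section 6.2.1 puts GRID mapping before any ablation.
- *Event starts before insertion and the subject is then enrolled.* Onset precedes the window, and no section says how to handle it. A site could even apply another sentence of 7.3.1: "Unchanged, chronic, non-worsening, or pre-existing conditions are not AEs and should not be reported". The subject is in the denominator, but the event may not be in the numerator.
- *Event starts before insertion and the procedure stops.* The subject is never enrolled. Section 7.3.1 creates no reporting duty and section 11.4 requires no CRF. By its name, the Enrolled Population would not include the subject.

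**Step 2: Table 2.** Its Enrollment/Baseline entry for adverse events permits recording before insertion. It is marked only as applicable and sets no start point. One site could follow Table 2 and another 7.3.1, so capture could differ by site. The Index Procedure cell for this row is blank in the text available to me. That may be a merged cell lost in conversion, and I draw nothing from it.

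**Step 3: scale, for illustration only.** Section 5.6 equates 20% of maximum enrolment with about 60 subjects, so N ≈ 60 / 0.20 = 300. The three AF-type caps in the same section give 3 × 110 = 330. Where the denominator is unchanged (second case), one missed subject is worth

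- 1/300 = 0.33 percentage points, or
- 1/330 = 0.30 percentage points.

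With an assumed 6 subjects with recorded events among 300, and m added subjects with pre-insertion events:

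| m | Second case: (6+m)/300, exact 95% CI | Third case: (6+m)/(300+m) |
|---|---|---|
| 0 | 2.00% (0.74 to 4.30) | 2.00% |
| 1 | 2.33% (0.94 to 4.75) | 7/301 = 2.33% |
| 3 | 3.00% (1.38 to 5.62) | 9/303 = 2.97% |
| 6 | 4.00% (2.08 to 6.88) | 12/306 = 3.92% |

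The intervals are Clopper-Pearson, the method in SAP 3.1.2. The counts 6 and m are assumptions.

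**Step 4: direction.** Restoring a missed subject with an event raises the rate in both cases. If the denominator becomes all attempted procedures, attempts stopped before insertion without an event pull slightly the other way: 6/301 = 1.99%. At a 2% rate it would take 49 such attempts to offset one restored event, since 7/(301 + 49) = 7/350 = 2.00%.

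**The case against.** The best case against the point has four parts.

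*The documents do not uniformly exclude these subjects.* Besides Table 2, section 5.5 lists becoming a screen failure after consent among the discontinuation reasons notified to the sponsor. Section 6.2.1 withdraws a subject whose procedure is aborted before a voltage map without requiring that the catheter was inserted. A reader might infer that access complications are simply left out of the adverse event table. The documents do not support that: their sections conflict, and with the ENR definition redacted the table's membership cannot be confirmed. This part stands, and it turns the point into an inconsistency with a probable gap.

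*The affected set is small.* Only events before insertion are at issue. The vessel-damage risk in section 15.2, "Damage to your blood vessels where the catheter may have scraped as it traveled to your heart", describes a catheter in transit; for the mapping catheter that is after insertion and so inside the window. Section 15.2 does also list bleeding or infection at the access site, but much of that would appear later and be captured. The protocol does not state which sheaths or catheters precede the GRID. This part also stands.

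*The consequence is limited.* Adverse events are additional data (Protocol 4.2, SAP 2.4.2), and SAP 3.3.3 plans no hypothesis testing. Section 15.3 names additional mapping as the only required element beyond standard care, so opening the window at insertion could be a deliberate choice. That is arguable, but it fits poorly with a reporting list that covers the whole mapping/ablation procedure.

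*There is a backstop.* Device complaints under 7.3.2 carry no enrolment condition. However, they concern device deficiencies, and that section says they are not collected on a study CRF, so they do not fill the gap.

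**Conclusion.** The point holds as a gap and a conflict between sections. Under the literal wording of Protocol 5.4, 7.3.1 and 11.4, a procedure-related event before mapping catheter insertion carries no reporting duty. A consented subject whose procedure stops for that reason is never enrolled and is probably outside the adverse event table. Table 2 suggests otherwise and does not settle the matter.

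Omitting such events biases the procedure-related rate downward. Its size cannot be derived from the documents. The one anchor is about 0.33 percentage points per missed subject at an assumed N of about 300 (0.30 at 330).

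A reader might go further and infer that a large share of events is lost. For example, if 0.5% to 2% of 300 attempts had an event before insertion (1.5 to 6 events) and 9 events were captured, the share missed would be 1.5/10.5 = 14% to 6/15 = 40%. The documents give neither rate. The sum also treats every pre-insertion event as missed, including those in subjects who are then enrolled and whose events a site might record. It should not be read as an estimate.

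This is a worthwhile improvement at low cost. It does not touch the primary endpoint or the mapping analyses.

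**What to change.** Reconcile Protocol 5.4, 7.3.1, 11.4 and Table 2 around one stated start point:

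- Start collection of procedure- and device-related events at the start of the index procedure in every consented subject, and say that this includes anaesthesia or sedation. A start at first vascular access could miss events from anaesthesia already under way.
- State that an event with onset before insertion is reported whether or not the subject is then enrolled, and extend the CRF rule in 11.4 to match.
- Report these events over all attempted procedures. Failing that, list attempted-but-not-enrolled subjects with their events separately from the ENR table.
- Keep the present definition of enrolment for the mapping and effectiveness analyses.

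The cost is a few sentences in the protocol, a matching line in SAP 3.2.4, and adverse event entries for a small number of subjects who are not enrolled. The reported event rate may be slightly higher.
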